1. OBJECTIVES

Duavee® is tissue specific estrogen complex of bazedoxifene plus conjugated estrogen which is FDA approved for relief of menopausal symptoms and prevention of osteoporosis in women with a uterus who have not been diagnosed with estrogen dependent neoplasia. The overall purpose of this research is to demonstrate in a preliminary fashion that despite reduction in menopausal symptoms, (Duavee®) does not increase and may decrease proliferation in benign breast tissue in a cohort of peri- or post-menopausal women at moderately increased risk for breast cancer. If this pilot shows rapid accrual, good retention, and lack of significant increase in the risk biomarker Ki-67 in benign breast tissue, a larger prevention trial is envisioned in the Southwest Oncology Group

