1.1 Primary Feasibility Objective

To determine feasibility for a larger clinical trial in women at moderately increased risk we will:

1.1.1 Determine if accrual is brisk as demonstrated by accrual of at least 20 moderate risk women in the initial 6 months (3.5 entrants per month) in a single institution;

1.1.2 Determine if there is a 15% or lower dropout rate over the 6 month intervention; and

1.1.3 Determine if 20% or fewer women with paired RPFNA specimens exhibit a meaningful increase in benign breast cell proliferation (Ki-67) where meaningful increase is defined as an increase in Ki-67 to 2% or higher in individuals with initial Ki-67 < 1% or a doubling of Ki-67 in individuals with initial Ki-67 of 1% or higher.

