3. SUMMARY OF STUDY PLAN

Peri- or post-menopausal women meeting the risk and medical eligibility criteria (see below) will undergo random periareolar fine needle aspiration (RPFNA) under the umbrella screening protocol HSC 4601. Women with at least 500 cells on their cytomorphology and/or Ki-67 slide, but with Ki-67 expression less than 4% will be eligible to proceed to the intervention phase of this study. At a baseline on-study visit, women will have a physical exam, DEXA for body composition, complete a 29 item Menopause Quality of Life Intervention Questionnaire [Lewis 2005] and hot flash assessment, have fasting blood obtained for biomarkers as well as to assure reasonable normal organ function. Key symptoms assessed at baseline will be hot flashes. Forty women will be entered on the treatment portion of the trial and will take Duavee® one tablet daily. Drug will be supplied by Pfizer. After 6-8 months of study agent, biomarkers will be reassessed. Mammogram, DEXA for body composition, RPFNA, and blood draw will be repeated. A complete side effects assessment will be performed. Entry of 40 women should allow 36 women to complete the study and be evaluable for the primary endpoint. Trial accrual is anticipated to take 6 months with completion of clinical aspects of the study by 12 months. Since this is not a blinded study, analysis of feasibility and changes in Ki-67 can take place immediately.

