8. CRITERIA FOR EVALUATION AND ENDPOINT DEFINITION

8.1 Primary Endpoint

Prior to formal analysis, there are two aspects of a feasibility trial that are based on simple numbers. If we cannot accrue 40 eligible women within a reasonable time (no more than 12 months) and/or if more than 15% of enrolled participants do not complete the study, then it would not be practical to propose future studies.

For the Specific Aim of documenting that Duavee® does not cause a meaningful increase in proliferation, only participants for whom paired specimens evaluable for Ki-67 will be included. An increase in Ki-67 will be defined by one of two scenarios: a) from a baseline Ki-67 <1% to a Ki-67 >2%; or b) for a baseline Ki-67 >1%, at least a doubling of the baseline value.

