13.2 Primary Feasibility Endpoints

The primary endpoint overall is an assessment of feasibility that will inform the decision about and the design of subsequent trials. This will be based on considerations of 1) ease of accrual of the target population; 2) acceptance and tolerability of the intervention. Basically, if either fail, then it would indicate that future trials with this approach are not feasible to consider

For the first aspect of accrual, a criterion has been set at 20 participants accrued in 6 months (starting from when the trial is actually open to enrollment). If the accrual rate is slower than this, it would be impractical to conduct a similar trial at a single institution. While total accrual will be used for this initial criterion, the relative ease of accrual into the two cohorts (Cohort A, Ki-67<1%; Cohort B, 1% ≤ Ki-67 < 4%) will be taken into consideration. Certainly it is anticipated that accrual to Cohort A will be easier and faster, but if accrual to Cohort B is not at least half the overall rate (i.e., 20 participants per 12 months) then it would indicate that a trial requiring measurable Ki-67 >1% would not be a feasible option. For this assessment, accrual is considered as meeting all eligibility criteria, signing an informed consent, and receiving the first dose of study agent. This number will then be used for consideration of the second feasibility aspect.

The second aspect of feasibility is retention of participants on trial, completion of the planned 6 months of intervention, and acquisition of repeat RPFNA specimen (plus blood, mammogram, etc.) for assessment of modulation in quantitative biomarkers. A criterion has been set at 85% completion overall. While the ultimate goal is paired samples for comparison of biomarkers (for sample size and power calculation purposes), a high incidence of early problems with participant compliance in general (adverse events, complaints about the study agent or the schedule, etc.) would serve as an indication that the intervention would not be suitable for future trials.

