The above criteria are intended to inform consideration of future biomarker trials with Duavee®; not to provide conclusive proof of principle. Thus, pre-set values for “success” or “failure” have been established; rather than a formal approach of statistical analysis and sample size power calculations. The total number of 40 participants represents a reasonable number for a pilot trial. Given our experience with similar biomarker trials using a variety of SERMs or an AI, this size

trial will readily document efficiency in accrual and identify problems with participant acceptance (compliance, retention, completion).

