13.3 Primary Quantitative Endpoint

The primary quantitative (but secondary overall) endpoint addresses the specific question that Duavee® might produce the deleterious effect of increasing breast cell proliferation. While there is no evidence for this (and the FDA does not consider this a risk to be included in labelling) it is still a perceptual concern by women and providers. Thus, an assessment will be made of the frequency of participants that exhibit a likely clinically meaningful increase in Ki-67. This will be defined differently for the two cohorts, but both will contribute to the analysis of potential increase. For Cohort A (initial Ki-67 < 1%), a meaningful increase is defined as any value of 2% or greater on the off-study aspiration. For Cohort B (initial Ki-67 \geq 1% but <4%), a meaningful increase is defined as a doubling or greater of the initial rate (i.e., a repeat aspiration value of at least 2%). Historically, for women in our High Risk Breast Clinic similar to those being enrolled in this study, approximately an 11% incidence of Ki-67 increasing is observed in the absence of any intervention. Therefore, with a minimum (per feasibility endpoint #2) of 34 paired specimens in which to assess change, an observed frequency of 10% or less would provide assurance that the true rate does not exceed 20% (95% confidence interval). Conversely, an observed frequency as high as 20% could still accommodate a true rate of 10%. Thus, as long as the observed frequency is \leq 20%, subsequent trials could be designed with a placebo-control arm. Only for an observed frequency >20% would it be impractical to design future biomarker trials.

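### With 34 pairs, three Ki-67 increases count as 10% or less but do not bound the true rate at 20% with 95% confidence; by exact limits, only two or fewer do

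*Combined protocol and SAP*

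**What the plan says.** Section 13.3 defines a meaningful Ki-67 increase for each cohort and cites a background rate of about 11% without intervention. It then reasons "with a minimum (per feasibility endpoint #2) of 34 paired specimens in which to assess change" and concludes that "an observed frequency of 10% or less would provide assurance that the true rate does not exceed 20% (95% confidence interval"). It gives no interval method, no sidedness and no count of women.

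The 34 comes from section 13.2, where "The total number of 40 participants represents a reasonable number for a pilot trial" and "A criterion has been set at 85% completion overall". Section 8.1 restricts the analysis: "only participants for whom paired specimens evaluable for Ki-67 will be included". Section 3 is more optimistic: "Entry of 40 women should allow 36 women to complete the study and be evaluable for the primary endpoint".

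The decision threshold is a different one. Objective 1.1.3 reads "Determine if 20% or fewer women with paired RPFNA specimens exhibit a meaningful increase in benign breast cell proliferation (Ki-67"), and section 13.3 likewise regards further trials as workable up to an observed 20%.

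**The concern.** A statement about an observed 10% or less has to hold at the largest count that satisfies it. With 34 pairs that count is 3, because 3/34 = 8.8% and 4/34 = 11.8%. Three events is too few for a normal approximation to be trusted, and the stated bound sits right at the edge of what 34 pairs can support.

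This is the only sentence in 13.3 that says what a favourable Ki-67 result would establish with confidence. Section 1 makes a clean Ki-67 result one condition for going further: "lack of significant increase in the risk biomarker Ki-67 in benign breast tissue, a larger prevention trial is envisioned". Taken at its word, 13.3 would let a result of 3/34 be reported as excluding a true rate above 20% with 95% confidence, when the exact interval reaches 23.7%, about twice the 11% background. The case is not remote. At the 11% rate, 3 is the most likely single count in 34 (47.7% − 26.2% = 21.5%).

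**Working it through.** **Inputs.** Enrolment 40 and completion 85% (13.2), so 40 × 0.85 = 34 pairs. Observed threshold 10%, bound 20%, confidence 95% and background rate 11% (all 13.3). Sidedness and method are not stated. An interval is naturally read as two-sided; one-sided limits are shown as well.

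**1. Reproducing the plan's figure.** The two-sided Wald upper limit at exactly 10% is

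p + 1.96 × √(p(1 − p)/n) = 0.10 + 1.96 × √(0.09/34) = 20.1%.

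That matches the printed 20%, so it is not a slip of arithmetic. But 10% of 34 is 3.4 women, which cannot be observed.

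**2. Exact limits at 34 pairs.** The Clopper-Pearson upper limit is the rate p at which P(X ≤ x | n, p) equals 0.025 (two-sided 95%) or 0.05 (one-sided 95%).

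| Increases of 34 | Observed | Exact two-sided upper limit |
|---|---|---|
| 0 | 0% | 10.3% |
| 1 | 2.9% | 15.3% |
| 2 | 5.9% | 19.7% |
| 3 | 8.8% | 23.7% |

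The exact one-sided limits are 17.4% at 2/34 and 21.3% at 3/34.

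**3. Other methods at 3/34.**

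| Method | Two-sided upper | One-sided upper |
|---|---|---|
| Clopper-Pearson | 23.7% | 21.3% |
| Wilson | 23.0% | 20.1% |
| Mid-P | 22.2% | 19.7% |
| Jeffreys | 21.7% | 19.3% |
| Wald, continuity-corrected | 19.8% | 18.3% |
| Wald | 18.4% | 16.8% |

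The two-sided Wald lower limit here is −0.7%, a sign that the approximation has broken down.

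**4. A check that needs no interval method.** If the true rate is 20%, the binomial probabilities for 34 pairs are 0.0005, 0.0043, 0.0178 and 0.0474 for 0, 1, 2 and 3 increases. Hence

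- P(3 or fewer) = 7.0%, above both 5% and 2.5%;
- P(2 or fewer) = 2.3%, below both.

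The 10% rule therefore gives about 93% one-sided assurance.

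**5. Other numbers of pairs.** The number of evaluable pairs is not fixed; 30 to 40 is assumed here. At the largest count within 10%:

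| Pairs | Count | Exact two-sided | Exact one-sided | P(count or fewer) at a true 20% |
|---|---|---|---|---|
| 30 | 3 | 26.5% | 23.9% | 12.3% |
| 34 | 3 | 23.7% | 21.3% | 7.0% |
| 36 | 3 | 22.5% | 20.2% | 5.2% |
| 37 | 3 | 21.9% | 19.6% | 4.5% |
| 39 | 3 | 20.9% | 18.7% | 3.3% |
| 40 | 4 | 23.7% | 21.4% | 7.6% |

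The two-sided exact limit is above 20% throughout; the one-sided limit is below 20% only with 37 to 39 pairs. The count of 2 is also specific to at least 34 pairs. With 33 pairs, P(2 or fewer) at a true 20% is 0.8³³ × (1 + 33 × 0.25 + 528 × 0.0625) = 0.000634 × 42.25 = 2.7%, just over 2.5%.

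**6. The companion sentence.** 13.3 also says that an observed rate as high as 20% could be compatible with a true 10%. At 6/34 (17.6%) the exact interval is 6.8% to 34.5%, so that statement holds.

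**The case against.** The strongest reply is that nothing operational depends on the sentence. The go rule is an observed 20% or less; 13.3 calls this endpoint secondary overall, and 13.2 sets its feasibility criteria without formal power calculations. Ruling out a rate above 20% is also in substance a one-sided question. On that reading the exact excess at 3/34 is only 1.3 points, Wilson is almost at 20%, and mid-P and Jeffreys fall below it. Clopper-Pearson is conservative, so part of the gap reflects the choice of method.

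Much of this stands, and it limits the weight of the point. The go rule is indeed untouched, the 20% does come from a recognised approximation, and the statement that only 2 or fewer will do applies to exact limits, not to every approximate one. It does not rescue the sentence. The disclaimer in 13.2 concerns accrual and retention, whereas 13.3 goes on to make an explicit 95% claim. The 7.0% tail at a true 20% fails the one-sided standard as well as the two-sided one, without relying on any interval method.

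**Conclusion.** The concern holds. With 34 pairs, the stated 95% assurance is met at 0, 1 or 2 increases and fails at 3, which still counts as 10% or less. The bound actually achieved at 3/34 is 23.7% (exact two-sided) or 21.3% (exact one-sided), not 20%.

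This rests on the 34 pairs that the plan itself uses and on exact binomial limits. The two-sided conclusion is the same for every number of pairs from 30 to 40; the one-sided conclusion changes only at 37 to 39. The fault is reliance on an unnamed normal approximation at a frequency that cannot occur, and it affects how a favourable result would be described. The go rule, the sample size and the companion sentence are sound on this point. It should be fixed, but it does not threaten the design.

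**What to change.** Replace the sentence in 13.3 with wording such as:

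> Using a two-sided 95% Clopper-Pearson interval on the pairs evaluable for Ki-67, with 34 such pairs the upper limit is 19.7% for 2 increases (5.9%) and 23.7% for 3 (8.8%). Two or fewer increases in 34 would therefore exclude a true rate above 20%.

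Also state that this interval will be reported for the actual number of evaluable pairs, since that number may differ from 34. Leave the companion sentence, the go rule and the sample size as they are.

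The cost is one sentence and no extra participants. The price is a less favourable stated assurance: at the 11% background rate the chance of meeting it drops from 48% (3 or fewer of 34) to 26% (2 or fewer). If the 10% threshold is to be kept, the alternative is to name the method and print the bound it delivers, about 24%.

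### The 20%-or-fewer Ki-67 mark works as a go/no-go for a controlled trial, but a pass cannot document that proliferation does not increase, and the 13.3 assurance at 10% or less fails with an exact interval

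*Combined protocol and SAP*

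**What the plan says.** The pass mark is set in Section 1.1.3: "Determine if 20% or fewer women with paired RPFNA specimens exhibit a meaningful increase in benign breast cell proliferation (Ki-67"), followed by the definition of a meaningful increase. Section 13.3 repeats the mark and gives its consequence. At or below 20% observed, "subsequent trials could be designed with a placebo-control arm". Above it: "Only for an observed frequency >20% would it be impractical to design future biomarker trials".

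Section 13.3 adds two statements about the true rate, each worked "with a minimum (per feasibility endpoint #2) of 34 paired specimens in which to assess change". An observed 10% or less is said to assure, by a 95% confidence interval, that the true rate is no higher than 20%. An observed 20% is said to remain compatible with a true 10%. The section also reports a historical rate of about 11% without intervention.

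Two other places describe the purpose of the Ki-67 endpoint more strongly. Section 8.1 gives the aim as "documenting that Duavee® does not cause a meaningful increase in proliferation". Section 1 makes "lack of significant increase in the risk biomarker Ki-67 in benign breast tissue" one of three conditions for a larger prevention trial, alongside accrual and retention. Section 13.1 likewise lists an absence of evidence of increased proliferation among the pre-set feasibility criteria. No pass mark other than the 20% is attached to this endpoint anywhere.

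**The concern.** The same figure, 20%, serves both as the true rate one would want to rule out and as the observed rate that still passes. A rule based on a point estimate passes about half the time when the truth sits at the cut-off. It can therefore screen for a go decision but cannot show that a rate is acceptably low.

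Section 13.3 describes the uncertainty at an observed 20% on the favourable side only. It does not say how high the true rate could be, and it gives no probability of passing when the drug does raise Ki-67.

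What is at stake is how a pass is reported. Section 2.2 says that stable proliferation alone would be a major advance, because women at increased risk and their physicians would probably be more comfortable using the drug. A reader who joins the 8.1 aim to the 20% mark would take a result such as 6/34 as support for that, when the data could not exclude a rate above 30%.

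**Working it through.** **Inputs.** Enrolment is 40 and the completion criterion 85% (Section 13.2: "A criterion has been set at 85% completion overall"), so 0.85 × 40 = 34 pairs, the minimum used in 13.3. Section 3 expects 36 evaluable women. The historical rate is 11% (13.3), and twice that is 22%.

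**Step 1: the plan's own figures.** The normal-approximation interval is p ± 1.96·√(p(1−p)/n), with n = 34.
- p = 0.10: 0.10 ± 1.96·√(0.10·0.90/34) = −0.1% to 20.1%. This matches the stated limit of 20%.
- p = 0.20: 0.20 ± 1.96·√(0.20·0.80/34) = 6.6% to 33.4%. This includes 10%, as stated. It also reaches 33%, which 13.3 does not mention.

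**Step 2: the attainable counts.** 10% of 34 is 3.4, so the largest count at 10% or less is 3/34 (8.8%). Its upper limits are:

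| Interval | Upper limit at 3/34 |
|---|---|
| Normal approximation, two-sided 95% | 18.4% |
| Wilson, two-sided 95% | 23.0% |
| Exact (Clopper-Pearson), two-sided 95% | 23.7% |
| Exact, one-sided 95% | 21.3% |

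Of these, only the normal approximation excludes 20%. The exact two-sided upper limit falls below 20% at 2/34 (5.9%; limit 19.7%) and not at 3/34. As a cross-check, under a true 20%, P(X ≤ 2) = 2.3%, which is below 2.5%, while P(X ≤ 3) = 7.0%, which is above it.

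**Step 3: what a pass means.** 20% of 34 is 6.8, so a pass is 6 or fewer. The largest passing count, 6/34 (17.6%), has an exact 95% interval of 6.8% to 34.5%.

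**Step 4: probability of passing.** P(pass) = P(X ≤ c), with X ~ Binomial(n, p).

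| True rate | 34 pairs, c = 6 | 36 pairs, c = 7 |
|---|---|---|
| 11% | 92.7% | 96.1% |
| 20% | 46.6% | 56.6% |
| 22% | 35.5% | 44.8% |
| 25% | 21.8% | 29.0% |
| 30% | 7.9% | 11.2% |

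Using 34 pairs does not exaggerate the problem: the chance of passing at a high true rate is larger at the expected 36.

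**Step 5: the likely result if the drug is inert at 11%, with 34 pairs.** P(0–2) = 26.2%. P(3–6) = 92.7% − 26.2% = 66.5%. P(7 or more) = 100% − 92.7% = 7.3%. The most likely outcome is therefore a pass that does not exclude 20%.

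**The case against.** The strongest defence is that Section 13.3 does not confuse the two uses of 20%. It separates three outcomes: assurance about the true rate at 10% or less observed, permission to design a placebo-controlled trial up to 20%, and no-go above that. A reader might infer that the plan treats any result of 20% or fewer as showing no meaningful increase. The documents do not support that. Section 13.3 says no such thing, Section 1.1.3 stands under a feasibility heading, and neither Section 1 nor Section 8.1 states the 20% figure for Ki-67. In 8.1 the aim introduces the analysis set and the definition of an increase. Section 1 also describes its demonstration as preliminary. All of this stands.

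It also stands that a lenient go rule suits a pilot. The next step would be a controlled trial, which is the design able to detect a harmful effect, and the chance of a false no-go at 11% is only about 7%.

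A reader might also infer that the trial passes 36% of the time when the drug doubles the background rate. That is not established. Section 13.3 describes the 11% only as Ki-67 increasing. It does not say that the figure used the two-cohort definition of a meaningful increase, or the same interval between aspirations. The 47% at a true 20% needs no such link.

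Two things remain. The only pre-set mark for this endpoint cannot deliver the aim named in 8.1. And the assurance tier, on which the three-outcome defence relies, fails at 3/34 with an exact interval. The caveat in 13.2 against reading the criteria as conclusive proof does not clearly help, because it refers back to accrual and retention, and Ki-67 is introduced only afterwards.

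**Conclusion.** The concern holds in a limited form. The 20% mark is sound as a go/no-go and unsound as evidence that Ki-67 does not rise. At 34 pairs it passes 47% of the time at a true 20%, 36% at 22% and 22% at 25%. A 6/34 result is compatible with true rates from 6.8% to 34.5%. The assurance tier in 13.3 should start at 2/34 or fewer, not at 10% or less.

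The figures assume independent participants, one common rate across the two Ki-67 cohorts, and at least 34 evaluable pairs. The exact-limit statements use a two-sided 95% interval. The one-sided exact limit at 3/34 (21.3%) leads to the same conclusion. Reading 22% as double the background assumes that the 11% follows the plan's definition of a meaningful increase.

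This is a matter of what may be concluded. It does not call the sample size, the conduct of the trial or the decision to proceed to a controlled trial into question.

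**What to change.** 1. Keep 20% or fewer observed as the go/no-go mark in 1.1.3 and 13.3.
2. In Sections 1 and 8.1, state that a pass means proceeding to a controlled trial and does not document the absence of an increase.
3. In 13.3, replace the assurance at 10% or less with a rule based on the exact two-sided 95% interval:
   - *rate above 20% excluded*, only if the upper limit is below 20% (2 or fewer of 34);
   - *go, increase not excluded*, for any other result up to 20% observed (3 to 6 of 34);
   - *no-go*, above 20% observed (7 or more of 34).

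   If the number of pairs is not 34, apply the upper-limit condition rather than the count.
4. Print the pass probabilities from Step 4 in 13.3, and give both ends of the interval at the cut-off.
5. State whether the historical 11% uses the meaningful-increase definition.

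The cost is a few sentences and one table, with no change to participants, sample size or procedures. The downside is that a pass supports a weaker claim. If the drug is inert at 11%, the chance of being able to report that a rate above 20% is excluded is only about 26% with 34 pairs.
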